- Use of insulin pump in the last 6 months
- Age ≥ 18 to ≤ 40 years
- HbA1c $\leq 8.5\%$ if measured at screening or available from historical medical report performed within the last 6 months; in absence of a valid HbA1c measurement, average blood glucose estimated from CGM data to be approximately 200 mg/dL or less
- Absence of perimenopausal/menopausal symptoms
- Willingness to keep track of beginning of menstrual cycle
- Willingness to keep track of ingested carbohydrates
- Willingness to not become pregnant during study participation
- Regularly menstruating (at least every month with no missed cycles)
- Only free-cycling participants: willingness to use ovulation kits to confirm ovulation
- Only participants under oral contraceptive therapy: use of monophasic pill, with 3 weeks of active pill and 1 week of placebo
- Willingness to use the study Dexcom G6 during the study
- Participants must have Internet access and computer system that meets the requirements for uploading the study equipment

2. List the criteria for exclusion

- Pregnancy
- Hormonal birth control therapy except monophasic pill contraceptive
- Polycystic ovary syndrome (PCOS) diagnosis
- Current use of steroids
- Concurrent use of any non-insulin glucose-lowering agent (including GLP-1 agonists, pramlintide, DPP-4 inhibitors, SGLT-2 inhibitors, sulfonylureas, metformin)
- Uncontrolled thyroid disease
- Active fertility treatment
- Concomitant disease or condition that may compromise patient safety or ability to follow the protocol including: planned or current dialysis treatment; moderate to advanced nephropathy; known or suspected allergy to medical grade adhesives.
- Severe hypoglycemia or diabetes ketoacidosis (DKA) in the previous 6 months

3. List any restrictions on use of other drugs or treatments.

INSTRUCTIONS: List only those drugs or treatments that are prohibited while on study, not those listed as an exclusion criteria.

None

Statistical Considerations

1. Is stratification/randomization involved?

No

► IF YES, describe the stratification/ randomization scheme.

INSTRUCTIONS:

The stratification factors and/or the randomization plan should be identified. If there is no randomization component or important patient characteristics that will be used in treatment allocation or data analysis, a statement to this effect should be included.

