This observational trial is not powered to a specific outcome. A sample size of 40 females has been chosen with the purpose of being able to compute the Cohen's *d* metric once the trial is completed. Cohen's *d* is defined as the difference between two means divided by a standard deviation for the data (standardized difference between two means), and will serve as effect size to appropriately power the subsequent main trial.

3. Provide a justification for the sample size used in this protocol.

Include sample size calculations or statistical power estimation. If not applicable, please provide explanation.

IRB-HSR# 190046: Glycemic Profiles And Insulin Delivery Across The Menstrual Cycle In Women With Type 1 Diabetes

NCT04665999

Also include the anticipated accrual rate, the accrual goal for the study, including accrual goals by strata if appropriate, adjustments for drop-outs etc. and study duration.

The sample size is determined based on the fact that this study is a pilot trial including two groups (i.e., free-cycling females and females using oral contraceptives).

4. What is your plan for primary variable analysis?

Include primary outcome(s)/predictor variable(s), statistical methods/models/tests to be employed, or descriptive summaries as appropriate. If not applicable, please provide explanation.

The primary variable will be insulin sensitivity (SI) computed using a Kalman filter-based algorithm embedding a model of glucose-insulin dynamics; SI will be tracked over the duration of the menstrual cycle and compared between phases.

5. What is your plan for secondary variable analysis?

Include the following:

--Secondary outcome(s)/predictor variables, statistical methods/models/tests to be employed, or descriptive summaries as appropriate. If not applicable, please provide explanation.
--For phase III studies, the power/precision of the study to address the secondary objective(s).

Secondary variables will include metrics to quantify glycemic variability (e.g., percent time spent in different glycemic ranges, low/high blood glucose indices, coefficient of variation).

6. Have you been working with a statistician in designing this protocol?

Consultation with a professional statistician is highly recommended to ensure good science of the study and facilitate the review process.

No

IF YES, what is their name?

Answer/Response:

7. Will data from multiple sites be combined during analysis?

No

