Participants will be screened and inclusion/exclusion will be reviewed. A urine pregnancy will be performed. The subject will also be asked for their medical history, preferably with a physical exam, will be requested but not required. Height, weight, and vitals may be self-reported. Medical history may be obtained from data collected during prior clinical studies conducted from the past 24 months at CDT. Subjects will also have an HbA1c test completed upon enrollment. If the screening is performed remotely, the pregnancy test will be mailed to the participant. The

IRB-HSR# 190046: Glycemic Profiles And Insulin Delivery Across The Menstrual Cycle In Women With Type 1 Diabetes

NCT04665999

pregnancy test must be negative to proceed in the trial. While optional, participants will be asked to provide 3-months of pre-study personal CGM data.

Eligible participants will start a 3-month home data collection. During data collection, subjects will be asked to use a study-provided Dexcom G6 continuous glucose monitor, personal insulin pump, and a study-provided activity tracker. Participants who are not on oral contraceptive will be asked to use an ovulation kit to confirm ovulation. All participants will be asked to record the carbohydrates consumed each day (i.e. meals, snacks, carbohydrate treatments). Unbolused carbohydrates will be recorded in the Dexcom app or receiver, not in the participant's insulin pump. Participants will also be instructed to record Day 1 of their menstrual cycle each month into the Clue App. Free cycling participants will be asked to enter the monthly ovulation test results in the app as well.

Some study participants have prior use of diabetes data aggregators (e.g., Tidepool, Nightscout) and do want to switch to another data aggregator. The study team did not request that they use Tidepool or Nightscout; however, so not to interrupt their standard of care, the study may access study data stored at Tidepool and Nightscout in order to save it on a UVA server for analysis. This may require participants sharing personal login information to the study team to access data or study participants may share this data with the team.

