If the subject owns a personal laptop device, the participant will be asked to bring it to the visit for the study team to download specific software to be used during data collection if an in person screening is performed; otherwise, the study team will instruct the subject how to download the software from online website or the study team may provide the subject with a memory drive (USB) storing the appropriate resources to be used at home will be provided. Participants will be instructed on how to upload the equipment (i.e. insulin pump, CGM, Activity Tracker, Clue App, etc.). Participants will be asked to provide uploaded data periodically during the data collection period (approximately 1-2 times per month) using a local diabetes device management software (e.g., Dexcom Studio). Subjects will have the option of using their personal smartphone or receive a study smartphone to use in order to collect the data from the devices.

Participants will be asked to wear the study activity monitor during the data collection phase. Participants will also wear the activity monitor to collect information on activity, exercise, heart rate, and sleep. The commercially available app associated with the activity monitor will be placed on the smartphone to facilitate weekly downloading of data.

IRB-HSR# 190046: Glycemic Profiles And Insulin Delivery Across The Menstrual Cycle In Women With Type 1 Diabetes

NCT04665999

The study team will contact the participant via phone/email/text at least one time month to assess:

- Adverse events and device issues
- Review download of CGM and activity monitor to assess occurrence of glucose values <60 mg/dL and >300 mg/dL
- Verify Clue App monthly download – the study team logging into the subject's study account to verify its use and download data

Study Schedule

	Screening	Monthly Monitoring	Final
Study Days	1*	2-90	~90
Visit	1	2,3,4	5
Informed consent	x		
Review study eligibility	x		
Medical history (optional)	x		
Pregnancy test	x		x
Physical exam (optional), height, weight, and vital signs (self-reported)	x		
HbA1c	x		x
CGM use	x		
Activity tracker use		x	
Ovulation test (if applicable)		x	
Record menses in app		x	
Data uploads provided to study team		x	x
Monthly check-ins with staff		x	
Return study equipment			x

* Visit 1 may be split over 2 days

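### No menses date is taken before Day 1 or after about Day 90, so opening follicular days of free-cycling women and the pre-study CGM can be placed in the cycle only approximately

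*Combined protocol and SAP*

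**What the plan says.** The analysis is defined by the cycle. Statistical Considerations, item 4, states for the primary variable that "SI will be tracked over the duration of the menstrual cycle and compared between phases". No minimum number of cycles is set.

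Collection is defined by the calendar. Study Procedures, item 1: "Eligible participants will start a 3-month home data collection". The Study Schedule places monitoring on study days 2 to 90 and the final visit at about day 90. Neither entry nor exit is tied to a cycle day.

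Menses dates are collected only in that window. The instruction, "Participants will also be instructed to record Day 1 of their menstrual cycle each month into the Clue App", belongs to the description of home collection, and the schedule row "Record menses in app" is marked under monthly monitoring, not at screening or the final visit. Free-cycling women also enter ovulation test results. Medical history at screening is optional and names no last-menses date. No contact after the final visit is described.

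On earlier data: "While optional, participants will be asked to provide 3-months of pre-study personal CGM data". No menses dates, ovulation results, insulin records or meal records are requested with it.

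Eligibility fixes the cycle length of the pill group: "use of monophasic pill, with 3 weeks of active pill and 1 week of placebo", which is 28 days. Free-cycling women must menstruate regularly, at least monthly, but no day count is given.

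**The concern.** A woman may enter on any day of her cycle, so her opening stretch has no recorded start and her closing stretch has no recorded end. The Background contrasts luteal insulin requirements with those of the early follicular phase, so early follicular days are the reference. If a free-cycling woman enters before ovulation, her ovulation result and next menses mark where that follicular stretch ends, but nothing marks where it began. Early and late follicular days then have to be guessed apart, or the days dropped.

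Pill users on a fixed 28-day pack can largely be counted back, so the loss falls mainly on one of the two groups being contrasted. Statistical Considerations, item 2, says that the study is to yield a Cohen's d for sizing a later trial. Avoidable phase misassignment adds noise to that estimate. The pre-study CGM, as requested, also lacks the date that would let it serve a cycle-based question.

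**Working it through.** The plan states no number of cycles per woman, so there is no figure to reproduce.

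**Inputs.** Window W = 90 days (Study Schedule). Cycle length L = 28 days for pill users (21 + 7, inclusion criteria). For free-cycling women L is assumed, and 28 and 35 days are shown. Further assumptions: entry equally likely on any cycle day, constant L within a woman, and a 14-day luteal phase.

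**1. Full cycles in the window.** Let the first recorded onset be Day d, with d = 1 to L. Full cycles = onsets inside the window minus 1.
- L = 28: onsets at d, d+28, d+56 and d+84. The fourth is inside the window if d ≤ 6. P(3 cycles) = 6/28 = 21.4%; P(2) = 78.6%. Mean = 90/28 − 1 = 2.21. Share of days outside a full cycle = 28/90 = 31%.
- L = 35: the third onset is inside if d ≤ 20. P(2) = 20/35 = 57%; P(1) = 43%. Mean = 90/35 − 1 = 1.57. Share outside = 35/90 = 39%.
- At L = 30 every woman has exactly 2. At L = 26, 54% have 2; at L = 25, 40%.
- The window is approximate. At L = 28 the share with two or fewer is 82% for 89 days and 71% for 92 days.

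**2. What the extra dates do to that count.** If the next Day 1 is known, an onset on Day 91 closes a cycle that ends on Day 90. The condition becomes d ≤ 7, P(3) = 7/28 = 25%, and the share with two falls only from 78.6% to 75.0%. A last-menses date adds no full in-study cycle.

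**3. Opening follicular days with no recorded start (free-cycling).** With follicular length F = L − 14, a woman who enters at cycle time u < F contributes F − u such days. Averaged over u uniform on 0 to L, this is F²/(2L).
- L = 28, F = 14: 196/56 = 3.5 days; 3.5/90 = 4% of the window. Expected follicular days are 90 × 14/28 = 45, so 3.5/45 = 8% of them.
- L = 35, F = 21: 441/70 = 6.3 days; 6.3/90 = 7% of the window. Expected follicular days are 90 × 21/35 = 54, so 6.3/54 = 12% of them.

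**4. The other edges.**
- Entry after ovulation: days can be counted back from the first recorded menses. They lack an ovulation result, and a last-menses date would not supply one.
- Closing stretch: days can be numbered forward from the last recorded Day 1 and split at ovulation if that was reached. The next Day 1 is needed to normalise cycle length or to subdivide the luteal phase.

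**5. Counting back without dates.** If an onset k cycles back is estimated from the mean of n observed cycles, with within-woman SD s, the error SD is s·√(k + k²/n). Assumed s = 2 or 3 days:

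| s | n | k = 1 | k = 3 |
|---|---|---|---|
| 2 | 2 | 2.4 | 5.5 |
| 2 | 3 | 2.3 | 4.9 |
| 3 | 2 | 3.7 | 8.2 |
| 3 | 3 | 3.5 | 7.3 |

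The error is about 2 to 4 days one cycle back and 5 to 8 days three cycles back.

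**6. What dated pre-study CGM could add.** Over an unbroken 180 days, mean full cycles = 180/28 − 1 = 5.4 or 180/35 − 1 = 4.1, against 2.2 and 1.6 in step 1. This applies only to the CGM metrics, and only to women who supply the data.

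**The case against.** The case against making much of this is strong in several respects.

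- A reader might infer that the missing dates are why most women give two full cycles or fewer, and that recording them would recover the 31% to 39% of days outside a full cycle. Steps 1 and 2 show otherwise: the count follows from a 90-day window not aligned to the cycle. Those figures do not measure this gap.
- The primary comparison is between phases and requires no full cycle. Most days in the part-cycles can be assigned from recorded menses or ovulation. This stands, and it reduces the loss to the opening follicular stretch, which can itself be partly dated by counting back.
- A reader might infer that the pre-study CGM cannot be placed in the cycle at all. That is too strong. Steady pill users can be counted back on a 28-day pack, and free-cycling women can be placed with growing error. The plan also assigns that CGM no analysis, so no stated use fails.
- The imbalance between groups depends on the assumed free-cycling length, and no bias has been shown. The study is an unpowered pilot.
- Staff may learn the last-menses date when they check menstrual regularity at screening. They may, but the plan does not require it to be recorded, and the app data are downloaded from a study account with no stated import of earlier entries.

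What survives is narrow: a date that is easy to collect is not collected, and it matters most where counting back is least reliable.

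**Conclusion.** The point holds as a cheap improvement of modest size. Followed as written, the plan leaves an average of 3.5 of 90 days (L = 28) to 6.3 of 90 days (L = 35) per free-cycling woman in which early and late follicular days cannot be reliably separated. This rests on random entry, a 14-day luteal phase and assumed cycle lengths, since the protocol gives none for this group. Pill users lose little if packs are taken without a break.

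The pre-study CGM can be placed only approximately: in free-cycling women the error SD grows from about 2 to 4 days one cycle back to about 5 to 8 days three cycles back, on an assumed within-woman SD of 2 to 3 days. That is coarse for assigning phases. The documents do not support a claim that the phase comparison is invalid or biased, or that a third of the data is lost for want of these dates.

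**What to change.** - At screening, record the date of the last menses and, where the woman tracks them, the Day 1 dates of the previous 3 months. For pill users, record pack start dates.
- After about Day 90, obtain the next Day 1 by text or through the app.
- State in the analysis plan that the last-menses date assigns cycle day to the opening in-study days in the SI analysis, and that the next Day 1 closes the last cycle.
- Use the dated pre-study CGM only for a supplementary, Day-1-aligned analysis of the glycemic variability metrics, labelled as lacking ovulation confirmation. It does not support SI, because no pre-study insulin or meal data are requested.

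The cost is one screening question and one message per woman, with no new visit, device or participant. The downside is that recalled dates are less accurate than dates entered at the time, which is a further reason to keep the pre-study analysis supplementary. The gain for the primary SI analysis is a few percent of days. This change does not raise the number of full in-study cycles. Guaranteeing three would mean collecting until the fourth recorded onset, up to 4L days (112 at L = 28, 140 at L = 35), which is a separate and costlier decision.
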